7.3.3. Covariates

Covariates to be evaluated using descriptive statistics and curated data formatted to the Sentinel Common Data Model (SCDM) include:

- Age in years at vaccination.
- Sex.
- Race (i.e., American Indian or Alaska Native, Asian, Black or African American, Native Hawaiian or Other Pacific Islander, White, Multiracial).
- Hispanic or Latino ethnicity (i.e., yes, no, or unknown).
- Concomitant vaccinations (e.g., influenza, COVID-19, varicella-zoster, pneumococcal vaccine) before, on the same date as, and after *Arexvy* vaccination.

- Immunocompromising conditions (defined by HPHCI: human immunodeficiency virus [HIV]/acquired immunodeficiency syndrome, hematologic malignancy and related conditions, solid malignancy except non-melanoma skin cancer, solid organ or stem cell transplantation, rheumatological/inflammatory conditions, and immune disorders) identified via ICD-10-CM diagnosis codes; some immune disorders may be restricted to those with both diagnosis codes and evidence of treatment (e.g., multiple sclerosis and systemic lupus erythematosus).
- Other comorbidities (e.g., diabetes mellitus, chronic kidney disease, chronic pulmonary disease, stroke, heart disease) identified via ICD-10-CM diagnosis codes.
- Recent infections that might precipitate GBS, ADEM, or AF (such as respiratory infections [including for example COVID-19, and those caused by *H. influenzae*, influenza virus, *Mycoplasma pneumoniae*], gastrointestinal infections [including those caused by *Campylobacter jejuni*, hepatitis E], and others [including for example those caused by Chikungunya virus, cytomegalovirus, Epstein-Barr virus, *Escherichia coli*, herpes simplex virus, herpes zoster virus, HIV, Japanese encephalitis virus]) [Jacobs, 1998; Tenembaum, 2007; Boos, 2020; Gundland, 2020; Parsons, 2020; Anderson, 2021] identified via ICD-10-CM diagnosis codes.
- Recent health care events or conditions that might precipitate GBS, ADEM, or AF (such as solid organ or stem cell transplantation, certain surgeries, trauma, obstructive sleep apnea, hyperthyroidism, myocarditis, pneumonia, sick sinus syndrome, panic disorders, metabolic syndrome, alcohol use disorder) identified via ICD-10-CM diagnosis codes and/or procedure codes.
- Concomitant medications that are known to cause GBS, ADEM, or AF.
- Research Partner
- Geographic region (Census Bureau Regions: Northeast, Midwest, South, West, Other)
- Calendar month/year of vaccination
- Healthcare utilization in prior 365 days (e.g., ambulatory visits, hospitalizations, medication dispensings)

Note that race and ethnicity data may be incomplete, and completeness will vary by RP. Patients with immunocompromising conditions will not require to receive treatment for their condition because this would increase the likelihood of misclassification.

7.3.4. Confounders and effect modifiers

The self-controlled nature of the SCRI design means that time-fixed traits will not act as confounders. However, it is important to consider potential time-varying confounders, particularly seasonality. *Arexvy* administration will have a seasonal pattern, the outcomes of interest may have seasonal patterns [Moutzouris, 2003; Loomba, 2015; Webb, 2015; Hamdani, 2023], and the combined risk and control windows are somewhat long.

Therefore, primary analyses will be conducted unadjusted for seasonality, but sensitivity analyses will be conducted for each outcome that adjusts for seasonality (note that it will likely not be possible to adjust for seasonality for ADEM given the need for adequate reference data). Details regarding these sensitivity analyses will be included in the SAP.

7.4. Data sources

This is a non-interventional safety study based on secondary use of data previously captured from consumers or healthcare professionals for other purposes. Data to be used in this study will include medical chart reviews (including follow-up on data with healthcare professionals) and electronic healthcare records. Patients will not be administered any vaccine as part of the study. Individual case AE/adverse reaction reports will not be generated from this study.

This post-authorization safety study will be conducted using health plan administrative claims data held by 5 RPs (i.e., Carelon, CVS Health, HealthPartners, Humana, Point32Health) who are participating in the US FDA's Sentinel System [Behrman, 2011]. All RPs are expected to contribute data for each analysis. In addition to providing claims data, the RPs will provide scientific input and feedback to support this study. The 3 large RPs currently refresh their data in the Sentinel Distributed Database multiple times per year and the 2 smaller sites refresh annually. For each analysis we will leverage the most recently available data or will work with the sites to adjust their schedule. Administrative claims data require time to accrue and approach completeness (approximately \geq 90% complete), and the amount of time depends on care setting, with inpatient diagnoses requiring ~6 months. RP data refreshes, including data quality checks following Sentinel System procedures, take approximately 1 month.

Each of the RP is discussed below with detail on the number of their members who are \geq 50 years of age:

FDA Sentinel System RPs: The FDA Sentinel System is an active surveillance system that utilizes electronic healthcare data from a distributed data network for monitoring the safety and effectiveness of regulated medical products in the US, established under the Sentinel Initiative [Behrman, 2011; Platt, 2018; Brown, 2022]. We will leverage the technical infrastructure of the FDA's Sentinel System, including the SCDM and the Distributed Database [Curtis, 2012]. This approach allows participating organizations to retain control of their data, ensure data and patient privacy and confidentiality, and enable the identical analysis to be conducted at each site. Importantly, the data and processes developed for Sentinel includes robust data quality checks and involvement of individuals within the RP organizations who have deep expertise in the source data. The provenance of the data included in this proposal is well understood and traceable. Each of the Sentinel RPs have demonstrated capability to obtain the majority of requested original medical records for review, which would permit adjudication of outcomes when this is necessary.

The national insurer populations, CVS Health (formerly Aetna), Elevance Health (formerly Anthem; Carelon Research is a subsidiary), and Humana, currently participate

in the FDA's Sentinel System, as does the regional integrated delivery system HealthPartners. The regional insurer, Point32Health, is the home organization of the Harvard Pilgrim Health Care Institute (HPHCI) and currently participates in the Vaccine Safety Datalink, funded by the Centers for Disease Control and Prevention (CDC).

Together, these RPs provide large, representative patient populations, extensive experience with similar research, and the ability to carry out the project according to the required timeframe.

• **CVS Health** is one of the nation"s leading healthcare companies that owns Aetna, a national Health insurance company that serves over 38 million people with information and resources to help them make better-informed decisions about their health care. CVS Health became an FDA Sentinel RP in 2010 and continues to be one of the largest contributors of data for public health purposes. As of

October 2023, there are approximately 4.4 million current members with both medical and drug coverage, who are \geq 50 years of age, and are research eligible. CVS Health offers Medicare Advantage.

- Carelon Research is a subsidiary of Elevance Health (formerly Anthem), the largest health benefits company in terms of medical membership in the US. Elevance Health is an independent Blue Cross and Blue Shield Association licensee. Carelon Research is the health services research entity for Elevance Health that integrates the public health, pharmacoepidemiologic, health outcomes, and pharmacoeconomic concerns of these companies and their clients to conduct outcomes analyses. Carelon Research includes approximately 68.4 million current members with medical and prescription drug coverage who are research eligible. As of December 2023, there are approximately 7 million current members with both medical and drug coverage, who are ≥50 years of age and are research eligible. Health plan members span the US, specifically, the Northeastern, Mid-Atlantic, Southeastern, Midwestern, Central, and Western regions.
- HealthPartners is an active collaborator and RP in the FDA Sentinel System. • HealthPartners is the largest consumer-governed non-profit health care organization in the country, providing care, coverage, research, and education to improve health and well-being in partnership with its members, patients and community. Included under HealthPartners' umbrella are Regions Hospital, HealthPartners Care Group, HealthPartners Center for Memory & Aging, Park Nicollet Methodist Hospital and HealthPartners Institute. HealthPartners has formal relationships with hospitals and clinics throughout Minnesota and western Wisconsin, including Westfields Hospital (New Richmond, WI), Lakeview Hospital (Stillwater, MN), Hudson Hospitals and Clinics (Hudson, WI), Amery Hospital and Clinic (Amery, WI), St Francis Regional Medical Center (Shakopee, MN), Hutchinson Health (Hutchinson, MN), TRIA Orthopedic Center, and Physicians Neck and Back Clinic. Founded in 1957, the HealthPartners family of care serves more than 1.8 million medical and dental health plan members. As of September 2023, there are approximately 247 000 current members with both medical and drug coverage, who are \geq 50 years of age, and are research eligible. HealthPartners is one of the top-ranked commercial health plans in

Minnesota and is also one of the highest rated plans in the nation, according to the National Committee for Quality Assurance's Health Insurance Plan Rankings 2021-2022.

- Humana is an active collaborator and RP in the FDA Sentinel System, the Patient-Centered Outcomes Research Institute's National Patient-Centered Clinical Research Network (PCORnet), and several distributed research network initiatives for vaccine safety. As of September 2023, Humana includes about 6.13 million members actively enrolled with both medical and prescription insurance coverage and who are research eligible. Among them, approximately 5.56 million are ≥50 years of age. Humana includes members throughout the US, with highest concentration of members in the South region.
- **Point32Health** is the second largest New England based health plan. It provides care to 2.2 million individuals under the names, Harvard Pilgrim Health Care and Tufts Health Plan. Harvard Pilgrim Health Care participated in the Sentinel System and Point32Health is currently a site for the CDCs Vaccine Safety Datalink. As of September 2023, there are approximately 248 000 current members with both medical and drug coverage, who are ≥50 years of age, and are research eligible. Although Point32Health is smaller than the other RPs, it has the important advantages of being the institutional home of HPHCI. HPHCI personnel have direct access to Point32Health's data, providing the ability to work directly with source data to understand apparent anomalies in any analyses performed within this distributed data network.

Specific information in the SCDM includes, but is not limited to, the following data:

- Enrolment data: One record per covered individual per unique enrolment span is included in the SCDM. Individuals are assigned a unique identifier by their insurer, which is linkable to all other data in the SCDM. Due to changes in employment status, individuals may be enrolled multiple times with the same insurer, and the length of each given enrolment span may vary substantially. Each record in the enrolment file indicates the patient identifier, enrolment start and end dates, and whether the patient was enrolled in medical coverage, pharmacy coverage, or both during that range.
- **Demographic data**, including birth date, sex, race (American Indian or Alaska Native, Asian, Black or African American, Native Hawaiian or Other Pacific Islander, White, or Multiracial), Hispanic ethnicity, and zonal improvement plan (ZIP) code of their most recently recorded primary residence.
- Immunization data are primarily captured via NDC and procedure codes in administrative claims data. We expect claims data to be a sufficiently complete source of exposure information for this *Arexvy* vaccine safety study since we expect its administration to be billed to payers and the SCRI design alleviates concerns about exposure misclassification. However, some of the participating RPs may link to state-based immunization information systems with varying levels of completeness and timeliness. Data from immunization registries will be included if available and permissible.

- **Pharmacy dispensing data**, including the date and NDC identifier for each dispensed prescription, the nominal days' supply, and the number of individual units (pills, tables, vials, etc.) dispensed. Products purchased out-of-pocket (i.e., not billed to insurance) are not captured.
- Medical encounter data, including the healthcare provider identified with the encounter as well as the facility in which the encounter occurred and its ZIP code. Admission and discharge dates (if applicable) are also included, as is the encounter type (either an ambulatory visit, an ED visit, an inpatient hospital stay, a non-acute inpatient stay, or an otherwise unspecified ambulatory visit). Discharge disposition (alive, expired, or unknown) as well as discharge status (where a patient was discharged) are also included for inpatient hospital stays and non-acute inpatient stays.
- Laboratory data, both tests and their results, are available for some laboratory tests. Depending on the need for laboratory test result data in the analyses, we will work with the RPs to assess completeness and quality of the tests.
- **Diagnosis data**, including the date of diagnosis, its associated encounter identifier, admission date, provider identifier, and encounter type. Diagnoses are recorded using (ICD-10-CM) diagnosis codes. For hospital and non-acute inpatient stay encounters, the SCDM includes both primary and non-primary (secondary or unknown) discharge diagnoses. Health outcomes and covariates are typically identified using ICD-10-CM codes alone or in combination with other elements, as appropriate, including dispensing date and laboratory test results.
- **Procedure data**, including the procedure date, its associated encounter identifier, admission date, provider identifier, and encounter type, are available. Procedures may be coded as: ICD-10 Procedure Coding System procedure codes; CPT categories II, III, or IV codes; revenue codes; or HCPCS levels II and III codes.

7.5. Study size

The sample size and power calculations are estimated for the primary outcomes of the study, GBS and ADEM, and the primary risk (days 1-42) and control (days 43-84) windows. In the US, background rates of GBS reported in the literature range from 1.6 to 6.3 per 100 000 person-years in the overall population. In those ≥ 60 years of age, the IRs vary from 2.4 to 4.7 per 100 000 person-years in studies conducted over several years between 1935 and 1987 [Law, 2021]. More recent publications are reporting IR ≥ 4 GBS cases per 100.000 person-years in older adults. A study conducted in the US on background rates of adverse events of special interest reported a GBS IR of 4.6 per 100.000 person-years in adults ≥ 65 years of age [Moll, 2023]. The background rate in the analysis conducted by [Lloyd, 2024] was 4.4 per 100,000 person-years (unpublished). Background rates of ADEM range from 0.3 to 0.6 per 100 000 person-years in the overall population [Pohl, 2016].

The estimated number of vaccinated individuals needed to detect an association between *Arexvy* and the outcomes, assuming 80% statistical power, a two-sided alpha = 0.05, and an equal duration of 42 days for the risk window and 42 days for the control window, are

reported in Table 8 for GBS and ADEM for a range of RRs to be detected and a range of IR for the outcomes. Table 9 is for AF and is based on risk and control windows of 8 days.

Using a background rate for GBS of 4.5 cases per 100 000 person-years (taken as the average from [Lloyd, 2024] (4.4) and Moll, 2023 (4.6)), a total number of 69 cases in the combined risk and control intervals provides 80% power to reject the null hypothesis of no association when the true RR is \geq 2.0. Approximately 4.4 million vaccinated patients are needed to accrue the number of cases of GBS (Table 8).

Using a background rate for ADEM cases of 0.45 per 100 000 person-years, a total number of 12 cases in the combined risk and control intervals provides 80% power to reject the null hypothesis of no association when the true RR is \geq 7.0. Approximately 3.9 million vaccinated patients are needed to accrue the number of cases of ADEM (Table 8).

In the US, an IR of 16.6 cases per 1000 person-years has been reported for AF in 2018 for those 55 years and older, with a range of 6.9 to 52.5 cases per 1000 person-years for those aged 55-64 and \geq 85 years of age, respectively [Williams, 2020]. For this secondary outcome, to detect a RR of \geq 2, 69 cases will be needed (Table 9).

Table 8Estimated number of cases and vaccinated health plan members
needed to detect an association between RSV vaccination and GBS
or ADEM using a SCRI design, with 80% power, a two-sided alpha =
0.05, under different scenarios for relative risk and background
incidence rate: 42-day risk and control window

Relativ e risk	Total number of cases (control and risk periods) *	Numbe r of cases in control period	0.3 per 100 000 PY	0.45 per 100 000 PY	0.6 per 100 000 PY	2 per 100 000 PY	3 per 100 000 PY	4 per 100 000 PY	4.5 per 100 000 PY	5 per 100 000 PY	6 per 100 000 PY
1.25	634	282	81746428 6	54497619 1	40873214 3	12261964 3	8174642 9	6130982 2	5449762 0	4904785 8	4087321 5
1.50	194	78	22610714 3	15073809 6	11305357 2	33916072	2261071 5	1695803 6	1507381 0	1356642 9	1130535 8
2.00	69	23	66672620	44448413	33336310	10000893	6667262	5000447	4444842	4000358	3333631
2.50	41	12	34785715	23190477	17392858	5217858	3478572	2608929	2319048	2087143	1739286
3.00	29	8	23190477	15460318	11595239	3478572	2319048	1739286	1546032	1391429	1159524
4.00	20	4	11595239	7730159	5797620	1739286	1159524	869643	773016	695715	579762
5.00	15	3	8696429	5797620	4348215	1304465	869643	652233	579762	521786	434822
6.00	13	2	5797620	3865080	2898810	869643	579762	434822	386508	347858	289881
7.00	12	2	5797620	3865080	2898810	869643	579762	434822	386508	347858	289881

*Total number of cases was calculated using the method described by Musonda et al. [Musonda, 2006], assuming that the length of the risk period is the same as the length of the control period.

Table 9Estimated number of cases and vaccinated health plan members
needed to detect an association between RSV vaccination and AF
using a SCRI design, with 80% power, a two-sided alpha = 0.05,
under different scenarios for relative risk and background incidence
rate (8-day risk and control windows)

Relative risk	Total number of cases (control and risk periods)*	Number of cases in control period	1 per 1000 PY	2 per 1000 PY	5 per 1000 PY	10 per 1000 PY	50 per 1000 PY
1.25	634	282	12875063	6437532	2575013	1287507	257502
1.50	194	78	3561188	1780594	712238	356119	71224
2.00	69	23	1050094	525047	210019	105010	21002
2.50	41	12	547876	273938	109575	54788	10958
3.00	29	8	365251	182626	73050	36525	7305
4.00	20	4	182626	91313	36525	18263	3653
5.00	15	3	136969	68485	27394	13697	2740
6.00	13	2	91313	45657	18263	9132	1827
7.00	12	2	91313	45657	18263	9132	1827

*Total number of cases was calculated using the method described by Musonda et al. [Musonda, 2006], assuming that the length of the risk period is the same as the length of the control period.

PY=person-years

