A secondary objective is to assess the risk of new-onset AF identified within 8 days after *Arexvy* vaccination.

Study Design

Self-controlled risk interval (SCRI) design.

Population

Health plan members \geq 50 years of age will be eligible if they: 1) received one dose of *Arexvy*; 2) had 365 days of continuous medical and pharmacy enrolment prior to *Arexvy* receipt; 3) had continuous enrolment through the end of the follow-up period; 4) had no evidence of a second dose of *Arexvy* during the follow-up period; and 5) had no evidence of another medical product indicated for RSV disease prevention prior to receipt of *Arexvy* or during the follow-up period.

Variables

Arexvy receipt; new-onset GBS; new-onset ADEM; new-onset AF.

Data sources

Five Research Partners (RPs) (Carelon, CVS Health, HealthPartners, Humana, Point32Health) participating in the United States (US) FDA's Sentinel System.

Study size

Using a background rate for GBS of 4.5 cases per 100 000 person-years, a total of 69 GBS cases in the combined risk and control intervals will provide 80% power to reject the null hypothesis of no association when the true relative risk (RR) is \geq 2.0. Approximately 4.4 million vaccinated patients are expected to be needed to accrue the number of cases of GBS. Using a background rate for ADEM of 0.45 cases per 100 000 person-years, a total of 12 cases in the combined risk and control intervals provides 80% power to reject the null hypothesis of no association when the true RR is \geq 7.0. Approximately 3.9 million vaccinated patients are expected to be needed to accrue the number of cases of ADEM.

Data analysis

SCRI-based analyses will use conditional Poisson regression to determine incidence rate ratios (IRRs) of outcomes with 95% confidence intervals (CIs).

Milestones

Data collection will begin **CC** (the month when vaccinations began) and continue through 30 June 2030 or until the number of cases needed to power the study with adequate precision have been accrued, whichever is earlier. An inferential analysis of each outcome will be conducted when the required number of cases have accrued. A final report will be submitted to the US FDA by 31 December 2031.

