Medical records will be obtained from participating RPs in a manner compliant with the Health Insurance Portability and Accountability Act (HIPAA) and local privacy regulations. Hospital and outpatient charts will be obtained directly through requests from RPs using identifiers obtained from administrative claims data. Designated protected health information users at each RP will link the protected health information with masked patient identification numbers, dates of birth, and provider information for the patients identified for medical record abstraction. As noted above, charts are not expected to be 100% obtainable from participating RPs and that ~30% of charts sought can be unobtainable based on prior experience. Section 7.7.2 includes description of how potential events with unobtainable charts will be handled in the analyses. Bias will not be expected based on whether charts were obtainable or unobtainable (reasons for charts being unobtainable include providers being non-responsive or providers incorrectly assuming patient authorization is required). Table 4 below summarizes the proposed diagnosis code-based case-finding algorithms and key elements of the validation of each outcome.

Table 4 Case-finding algorithms and risk and control windows for outcomes of interest

Outcome	Diagnosis code(s) to identify event	Event identification care setting and details	Risk window	Control window, Extra days	Look-back period for outcome-free window	Diagnosis code(s), care setting for outcome-free period	Published algorithm data	Chart review considerations
New- onset GBS	G61.0 ^a	CC1	Primary: 1-42 days [Sejvar, 2011; Goud, 2021; Britton, 2024 Lloyd 2024]	Control window: 43-84 days, Extra days: 7	-365 through - 1 (day 0 is day of event), as previously conducted [Polakowski, 2013]	G61.0 or G65.0, inpatient setting (any position)	 PPV from studies using Medicare data: (1) 78.57% (95% CI, 63.37%- 93.77%) [Goud, 2021] (2) 71.21% (95% CI: 63.49%-78.94%) 	Will seek charts on all events. Final analysis will include chart- confirmed events only.
			Sensitivity: (a) 1-21 days and (b) 8-28 days				[Arya, 2019]; (3) 68.0% (95% CI: 56.8%- 77.5%) [Lloyd, 2024]	

220149 (EPI-RSV-041 OA VS US DB) Protocol Amendment 2 Final

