7.7.2. Primary analysis

7.7.2.1. Main analytical approach

SCRI-based analyses of primary and secondary objectives will include the *Arexvy* vaccinees with an event of interest in the risk window, control window, or the extra days after the control. In these analyses, each individual serves as their own control. IRRs of the outcomes will be estimated with 95% CIs using conditional Poisson regression models. All SCRI-based analyses will use conditional Poisson regression. A forthcoming SAP will be finalized prior to conducting the inferential analyses.

Analysis of the primary GBS and ADEM outcomes will be based on chart-confirmed cases as has been previously done [Arya, 2019]. For those outcomes, onset of symptoms will be discerned from medical record review and date of the event will be classified based on expert clinician adjudication. Identification of all events in days 1 through 91 after vaccination will be included in the medical record review but which window (risk, control, extra days) the events are counted in for the analysis will be determined based on the symptom onset date from the medical record. Events identified in the claims data with unobtainable charts will be excluded from the primary analyses due to concerns about misclassification of the outcome and timing of onset of symptoms.

As previously noted, events among people who die during the follow-up window (risk window, control window, or during the extra days) will be included. The number of events will be quantified, if any, that were among people who died during follow-up. The final analyses will include individuals who die during the risk or control intervals.

Follow-up time will be artificially continued until the last day of the control interval, which will avoid including fatal cases that occurred in the control interval over fatal cases that occurred in the risk interval. If a fatal event occurs during the risk window, all the remaining days in the risk window and all the days that would have occurred in the control window will be included in the analyses.

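### The 4.4 million vaccinees stated for GBS allow for no chart loss; with the protocol's own 30% loss, 69 chart-confirmed cases need about 6.3 million

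*Protocol*

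**What the plan says.** Section 7.5 sizes the two primary outcomes for 80% power at a two-sided 5% level, with risk and control windows of 42 days each. For GBS it starts: "Using a background rate for GBS of 4.5 cases per 100 000 person-years". It asks for 69 cases in both windows combined at a relative risk (RR) of 2.0, then says: "Approximately 4.4 million vaccinated patients are needed to accrue the number of cases of GBS (Table 8". The Synopsis carries the same number: "Approximately 4.4 million vaccinated patients are expected to be needed to accrue the number of cases of GBS". For ADEM, at 0.45 per 100,000 person-years and RR 7.0, it asks for 12 cases and says: "Approximately 3.9 million vaccinated patients are needed to accrue the number of cases of ADEM (Table 8". Table 8 gives the exact counts as 4,444,842 and 3,865,080.

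On chart review, Section 7.3.2.1 says that about "30% of charts sought can be unobtainable based on prior experience" and that only confirmed cases enter the final primary analyses. Section 7.7.2.1 says: "Events identified in the claims data with unobtainable charts will be excluded from the primary analyses". Sections 7.3.2.2 and 7.3.2.3 say the same for GBS and ADEM separately.

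The Synopsis and Section 7.9.1 end data collection when the needed cases have accrued or in June 2030; the Synopsis adds that the earlier of the two applies.

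**The concern.** The vaccinee number and the primary analysis do not count the same cases. Table 8 turns cases into vaccinees as if each background case reached the analysis. The primary analysis keeps only cases whose chart was obtained and which were then adjudicated as confirmed.

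The protocol recognises this loss elsewhere. Section 7.3.2.1 oversamples for roughly 30% missing records in the AF validation, and Section 7.3.2.4 asks explicitly for 69 confirmed AF cases if the algorithm's positive predictive value (PPV) falls below 80%. The GBS and ADEM sizes have neither an allowance nor that label, and Section 7.9 names low vaccine uptake as the sample-size risk, not chart loss.

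What is at stake is the planning figure for a primary outcome. Anyone using 4.4 million to judge whether 69 analysable GBS cases can be reached by 30 June 2030 works from a number that is too small.

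**Working it through.** **Inputs from the protocol.** Two-sided alpha 0.05, power 80%, 42-day risk and control windows, GBS 4.5 and ADEM 0.45 per 100,000 person-years, RR 2 and RR 7 (Section 7.5); chart loss about 30% (Section 7.3.2.1); published GBS PPVs of 68.0% to 78.57% (Table 4).

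**1. Reproduce the case totals.** Table 8 cites the Musonda method. Its signed-root likelihood-ratio form with equal windows is

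n = (1.960 + 0.842·√B)² / A, where
A = 2·[RR/(1+RR)·ln RR − ln((1+RR)/2)] and
B = (ln RR)²/A · RR/(1+RR)².

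- RR 2: A = 0.1133, B = 0.9426, n = 68.09, rounded up to 69.
- RR 7: A = 0.6328, B = 0.6545, n = 11.02, rounded up to 12.

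The formula matches all nine rows of Table 8.

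**2. Reproduce the vaccinee numbers.** Vaccinees = control-window cases / (rate × 42/365.25).

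- GBS: 69/(1+2) = 23 control cases; 23/(4.5×10⁻⁵ × 42/365.25) = 4,444,842.
- ADEM: 12/(1+7) = 1.5 control cases, shown in Table 8 as 2; 2/(0.45×10⁻⁵ × 42/365.25) = 3,865,080.

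Both match exactly, so there is no hidden factor for retrieval or confirmation.

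**3. Apply 30% chart loss to GBS.** This takes every retrieved true case as confirmed, which is the favourable end.

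- Cases from 4,444,842 vaccinees at RR 2: 69 × 0.70 = 48.3.
- Power = Φ((√(n·A) − 1.960)/√B). At n = 69 it is 80.5%; at n = 48.3 it is 65.2%. With 48 cases, 80% power is reached only from about RR 2.3.
- Vaccinees for 69 analysed cases: 4,444,842/0.70 = 6.35 million, 43% above the stated figure.

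**4. Conditional range for GBS.** The protocol does not say whether 4.5 per 100,000 is a claims-based or a confirmed-case rate. If it is claims-based (assumption), the PPV applies as well:

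| Assumption | Confirmed cases at 4.44 million | Power at RR 2 | Vaccinees for 69 cases |
|---|---|---|---|
| 70% retrieval only | 48.3 | 65% | 6.35 million |
| 70% retrieval, PPV 78.57% | 37.9 | 55% | 8.1 million |
| 70% retrieval, PPV 68.0% | 32.8 | 49% | 9.3 million |

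**5. ADEM.** With 2 control cases, 3.87 million vaccinees correspond to 2 × (1+7) = 16 expected cases at RR 7, not 12. After 30% loss, 16 × 0.70 = 11.2 remain. Nominal power is 80.7%, because the unrounded requirement is 11.02. With the unrounded 1.5 control cases, 12 cases need 2.90 million before loss and 2.90/0.70 = 4.14 million after it.

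**The case against.** The strongest reply is that power here belongs to cases, not vaccinees. Each inferential analysis starts when the required cases have accrued, nothing stops accrual at 4.4 million, and the protocol calls the figure approximate. A reader might infer that the GBS analysis will have only 65% power. The documents do not support that: if 69 confirmed cases accrue, the stated power stands. This part of the reply holds, and it confines the point to the vaccinee number and to the case in which the June 2030 date comes first.

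The reply can also say that Table 8 already covers the shortfall. A 30% loss turns 4.5 into an effective 3.15 per 100,000, and the column for 3 per 100,000 shows 6.67 million. That is true, but those columns are labelled as background rates, and the text and Synopsis take their headline from the 4.5 column.

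The protocol also promises repeated retrieval attempts, says only that about 30% of charts can be unobtainable, and plans a sensitivity analysis that adds back events without charts. Better retrieval would shrink the gap. The sensitivity analysis does not add cases to the primary analysis, which is what the 69 cases are meant to power.

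Two further inferences go too far. One is that non-confirmation certainly removes another 21% to 32% of GBS cases. A PPV removes false positives, so it reduces accrual in full only if the 4.5 rate itself includes them, which the protocol leaves open. The other is that ADEM is clearly underpowered. Chart loss alone leaves nominal power near 81%, and Table 4 reports no ICD-10-CM-based ADEM algorithm from which a PPV could be taken.

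**Conclusion.** The point holds for GBS, and it is a point about the vaccinee figure. On the protocol's own 30% loss, 4.44 million vaccinees are expected to give about 48 chart-confirmed cases at RR 2, and about 6.35 million are needed for 69. The arithmetic in Table 8 is exact; what is wrong is that its result is presented as enough for an analysis that discards events without charts.

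This rests on 70% retrieval in both windows, on 4.5 per 100,000 being the rate of confirmable GBS, and on confirmation of every retrieved true case. If the rate is claims-based, the need is 8.1 to 9.3 million; that is a conditional range, not a finding. The 80% power is lost only if 30 June 2030 comes before 69 confirmed cases.

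For ADEM there is an inconsistency to note but no power shortfall to claim from chart loss: 3.9 million matches 16 expected cases, not 12, and 30% loss leaves about 11.2, just under the target.

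**What to change.** In Section 7.5, Table 8 and the Synopsis:

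- Say that the 69 GBS and 12 ADEM cases are chart-confirmed cases.
- Restate the GBS vaccinee number as about 6.3 million after 30% chart loss. Alternatively, keep 4.4 million and state that it is expected to give about 48 confirmed cases and about 65% power at RR 2.
- Say whether 4.5 per 100,000 is a claims-based or a confirmed-case rate. If claims-based, show 8.1 to 9.3 million as a range for PPVs of 78.57% down to 68.0%.
- For ADEM, note that 3.9 million comes from rounding 1.5 control cases up to 2, and give the unrounded need of about 4.1 million at 70% retrieval.

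The cost is protocol wording and one recomputed table. Design, windows, case targets and analysis do not change, but the stated GBS size becomes less favourable.
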